## **Primary Study Efficacy Endpoints:**

The primary efficacy endpoints for this study are:

- Histology-Based: Resolution of NASH OR Improvement in Fibrosis
- Clinically-Based: Time to first occurrence of the adjudicated events

#### **Schedule of Statistical Analyses:**

Statistical analyses of efficacy endpoints are planned to be performed at two study milestones:

- The Histology-Based primary endpoint will be analyzed at the time when the initially randomized 1000 subjects have performed the week 72 visit or terminated early.
- The Clinically-Based primary endpoint will be analyzed at EoS, when all 2000 subjects planned to be randomized into this study will receive Aramchol or matching placebo until EoS which will occur at the time when a total of 380 subjects will experience at least 1 pre-specified clinical event or at 5 years from last subject randomization, whichever comes first.

#### **Principal Analysis Set for Efficacy Inference:**

The principal analysis set for efficacy inference will be the Intention-to-Treat (ITT) Analysis Set which will include all randomized subjects as follows:

- The Histology-Based primary endpoint will employ the Histology-Based-ITT Analysis Set including all initially 1000 randomized subjects.
- The Clinically-Based primary endpoint will employ the Clinically-Based-ITT Analysis Set including all randomized subjects.

[figure not shown]
#### Type-I Error and Multiplicity Adjustment:

The overall alpha level for this study is 0.05 using 2-tailed tests. All significance testing for this study will use two-tailed tests.

[figure not shown]
The Histology-Based primary endpoint will use an alpha level of 0.02 and adjustment for multiplicity for the two alternatives proposed (Resolution of NASH, or, Improvement in Fibrosis) will use the Truncated Hochberg's procedure with gamma=0.1.

The Clinically-Based primary endpoint will use an alpha level of 0.03, or 0.05 in case that both alternatives proposed for Histology-Based primary endpoint were met (no key secondary endpoints are defined for the Histology-Based study part). The sole key secondary endpoint for the Clinically-Based study part will use the alpha level used for the Clinically-Based primary endpoint in case that the later "wins".

[figure not shown]

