Results showed a statistically-significant reduction in liver fat with Aramchol 400mg (p=0.0450) but not with 600mg (p=0.0655) compared to the placebo arm, despite similarity in the magnitude of treatment effect in the 400mg and 600mg arms. A post-hoc analysis showed statistically-significant  $\geq$ 5% absolute reduction in liver fat in 47% of patients treated with Aramchol 600mg vs. 24% with placebo (p<0.028) and 37% with 400mg, suggesting a dose-response pattern.

Biopsy results, key for further assessment in a NASH pivotal study, showed that significantly more patients treated with Aramchol 600mg vs. placebo achieved NASH resolution without worsening of fibrosis (16.7% vs. 5.0%; p=0.0514); and that a larger proportion of patients showed at least a one point improvement in fibrosis stage without worsening of NASH in Aramchol 600mg vs. placebo (29.5% vs. 17.5%; p=0.2110). Only 1 patient (1.3%) progressed to cirrhosis in the Aramchol 600mg arm whereas 6 (7.5%) and 3 (7.5%) patients reached this endpoint in the 400mg and placebo arms, respectively.

Both doses significantly reduced alanine aminotransferase (ALT) (p<0.001), aspartate aminotransferase (AST) (p=0.002) and HbA1c (p<0.007) vs. placebo in a dose-dependent manner.

Aramchol continued to show a favorable safety and tolerability profile. No death was reported in the study. SAEs were reported in approximately 10% of subjects. Each SAE was reported for a single subject, SAEs were typical for the patient population and no clustering of event types was noted in the active-treatment arms. Most AEs in the study were mild and recovered.

For a detailed description of the clinical and non-clinical development program of Aramchol refer to the current IB.

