Following the conduct of the Histology-Based milestone analyses, major findings may be publicly disseminated by the Sponsor in accordance with 21 CFR 312.7. To preserve study blinding, trial integrity, subject's adherence and retention, only grouped level summary of results of the Histology-Based analyses including key secondary as well as potentially exploratory endpoints planned to be analyzed at this study milestone will be disseminated. Summary safety findings will also be disseminated.

Study integrity and blinding will not be compromised by the public dissemination of information due to the following major reasons: 1) the individual subject treatment assignment and data listings will only be shared with the Sponsor's dedicated taskforce and with regulatory authorities. 2) The publicly disseminated information will be on a "by group" basis. 3) The observed proportions of Histology-Based outcomes will not allow determining individual subject assignment. 4) The observed proportions of adverse events will not allow determining individual subject assignment.

A more detailed Statistical Analysis Plan (SAP) covering the analyses of the Histology-Based data as well as the Clinically-Based data at EoS was submitted prior to study initiation. SAP amendment will also be prepared and submitted prior to revealing of the blind for the analysis of the Histology-Based data.

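### Truncated Hochberg with gamma=0.1 tests the larger histology p-value at 0.011 instead of 0.02, and the visible rule makes no use of the 0.009 this leaves after a single win

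*Combined protocol and SAP*

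**What the plan says.** The rule stands in the Synopsis under Type-I Error and Multiplicity Adjustment.

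- Overall level: "The overall alpha level for this study is 0.05 using 2-tailed tests".
- Histology family: "The Histology-Based primary endpoint will use an alpha level of 0.02". For its two alternatives (resolution of NASH, improvement in fibrosis) the adjustment "will use the Truncated Hochberg's procedure with gamma=0.1".
- Clinical endpoint: 0.03, "or 0.05 in case that both alternatives proposed for Histology-Based primary endpoint were met".
- Other possible users of histology alpha: "no key secondary endpoints are defined for the Histology-Based study part".
- The one key secondary endpoint, 5-year improvement in fibrosis, takes whatever level the clinical primary endpoint used, provided that endpoint succeeds.

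Section 8.4.3, on disseminating the Week-72 findings, speaks of "results of the Histology-Based analyses including key secondary as well as potentially exploratory endpoints planned to be analyzed at this study milestone". That does not fit the synopsis, which says there are no histology key secondary endpoints. The same section adds: "SAP amendment will also be prepared and submitted prior to revealing of the blind for the analysis of the Histology-Based data".

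The visible text does not define gamma, and the body of Section 11.2.4 is not visible in the public version.

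**The concern.** Truncating Hochberg is a trade. The threshold for the larger p-value is lowered so that, if only one hypothesis in the family is rejected, part of the family's alpha can pass to a later test. Here the price is paid and nothing is received. There is no histology secondary endpoint to take the alpha, and the clinical endpoint gains only after two wins.

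A single win is a planned success, because the histology endpoint is defined as either alternative (Sections 4.1.2 and 11.2.2). The cost falls on meeting both alternatives. That affects the strength of the histology claim, and it is also the event that raises the clinical alpha from 0.03 to 0.05. The 5-year fibrosis endpoint inherits the same level.

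**Working it through.** **The plan's own figure.** 0.02 + 0.03 = 0.05, which reproduces the overall level.

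**Thresholds.** For m = 2 ordered p-values, truncated Hochberg compares the i-th smallest with [γ/(m − i + 1) + (1 − γ)/m] × α. Here γ = 1 is ordinary Hochberg and γ = 0 is Bonferroni. With α = 0.02 and γ = 0.1:

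- larger p: (0.1 + 0.9/2) × 0.02 = 0.011 (ordinary Hochberg: 0.02)
- smaller p: (0.1/2 + 0.9/2) × 0.02 = 0.010 (ordinary Hochberg: 0.010)
- left over after exactly one win: 0.02 − 0.011 = 0.009

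Under the reverse reading of gamma, the larger p is tested at (0.9 + 0.1/2) × 0.02 = 0.019, and the loss in P(both) is at most 1.0 point.

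**Inputs for the size.** From the documents:

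- 1000 subjects at 2:1, so 667 vs 333
- Phase 2b rates in Section 3.2: resolution 16.7% vs 5.0%, fibrosis improvement 29.5% vs 17.5%
- 380 clinical events

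Assumed:

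- two weaker scenarios, both below the Phase 2b rates
- correlation 0.3 between the histology statistics, with unpooled variance
- clinical hazard ratio (HR) 0.75
- clinical statistic independent of histology

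**One marginal power, for orientation.** For fibrosis at the Phase 2b rates, the standard error is √(0.175·0.825/333 + 0.295·0.705/667) = 0.0273, so the expected z is 0.12/0.0273 = 4.40. Power is Φ(4.40 − 2.54) = 96.8% at 0.011 and Φ(4.40 − 2.33) = 98.1% at 0.02. Resolution is nearly certain at these rates, so these are also the values of P(both).

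**Joint results** (bivariate normal; γ = 0.1 → ordinary Hochberg):

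| Resolution; fibrosis | P(both) | P(at least one) | Exactly one, γ = 0.1 |
|---|---|---|---|
| 16.7 vs 5.0; 29.5 vs 17.5 (Phase 2b) | 96.8% → 98.1% | 100.0% → 100.0% | 3.2% |
| 12 vs 5; 25.5 vs 17.5 (assumed) | 64.1% → 72.3% | 95.9% → 96.2% | 31.8% |
| 11 vs 5; 24.5 vs 17.5 (assumed) | 47.6% → 57.0% | 88.7% → 89.3% | 41.1% |

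Over correlation 0 to 0.6 and pooled or unpooled variance, the loss in P(both) is 1.3–1.9 points in the first row, 7.7–10.4 in the second and about 9–11 in the third. A cruder approximation, with pooled variance throughout, gives 2.3 points in the first row. The largest change in P(at least one) in any setting is 1.0 point.

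**Clinical power.** Schoenfeld's formula is Φ(−ln HR × √(380 × 2/9) − z), with z the two-sided critical value. At HR 0.75 the first term is 2.644:

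| HR | α = 0.03 | α = 0.039 | α = 0.05 |
|---|---|---|---|
| 0.70 | 86.6% | 88.8% | 90.6% |
| 0.75 | 68.2% | 71.9% | 75.3% |
| 0.80 | 45.2% | 49.5% | 53.6% |

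**Averaged over histology outcomes, third scenario, HR 0.75:**

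- current rule: 0.682 × 0.524 + 0.753 × 0.476 = 71.6%
- ordinary Hochberg: 0.682 × 0.430 + 0.753 × 0.570 = 72.2%
- γ = 0.1 with 0.039 after one win: 71.6% + 0.411 × (71.9% − 68.2%) = 73.1%

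Across all settings the gains are 0.1–0.8 points (ordinary Hochberg) and 0.1–1.8 points (passing on 0.009).

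**Family-wise error.** Take one histology null and the clinical null as true, with a very large effect on the other histology alternative. The bound is 0.011 + 0.03 = 0.041 now. It is 0.02 + 0.03 = 0.05 under ordinary Hochberg and 0.011 + 0.039 = 0.05 with the carry-over. Simulation with histology correlation −0.5 to 0.9 gave 0.0405–0.0408, 0.0493–0.0495 and 0.0494–0.0497 respectively. With all nulls true, no option exceeded 0.0493. With only the clinical null true, every option gave 0.0498–0.0502, which is nominal within simulation error.

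**The case against.** **Hidden text.** The synopsis is a summary, and the body of Section 11.2.4 and the detailed SAP are not visible. Gamma may be defined there, and a single-win rule may exist. That is a fair limit. But the synopsis states when the clinical level is 0.03 and when it is 0.05, so a hidden third level would contradict it and the two would need to be aligned. The missing definition of gamma is not, by itself, a fault.

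**Small effect, assumed scenarios.** No planned histology rates or hazard ratio are visible. At the only rates given, P(both) loses under 2 points by the main calculation. The larger losses come from assumed effects. Even the Phase 2b anchor is loose: it comes from 600mg once daily for 52 weeks, in a population of which 60% had stage 2 or 3 fibrosis. The model also uses simple proportions in 1000 complete subjects, where the plan uses failure rules, multiple imputation and stratified CMH. The 380 events may not be reached before the 5-year limit. All this stands as a limit on the power figures; it does not touch 0.011 or 0.009.

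**Independence.** Histological progression to cirrhosis counts as a clinical event, and the first 1000 subjects enter both analyses, so the averaged clinical gains are approximate. Error control does not hinge on independence: family-wise error stayed at or below 0.05 for ordinary Hochberg and for the carry-over with the clinical statistic correlated 0 to 0.6 with histology.

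**A conservative procedure is not an error.** True. Thresholds close to Bonferroni also lean less on Hochberg's dependence condition. That bears on which remedy to choose; it is no reason to leave the 0.009 unused.

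**Conclusion.** The point holds as a matter of efficiency, not validity. Under the visible rule and the usual convention for gamma, the larger histology p-value is tested at 0.011 where 0.02 was available, and the 0.009 left after one win has no recipient. This arithmetic is exact.

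The loss in P(both) is 1.3 points at the Phase 2b rates and 8 to 9 points in the two weaker scenarios at correlation 0.3. The either-endpoint histology criterion is almost untouched, and average clinical power moves by less than 2 points. These sizes rest on the assumed effects, HR 0.75, all 380 events and independence of the clinical statistic.

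The benefit is modest, but ordinary Hochberg and the 0.039 carry-over each reject everything the current rule rejects, and sometimes more, within the same 0.05.

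**What to change.** Before the histology unblinding, define gamma, state the clinical alpha after exactly one histology win, and adopt one of the following. They are alternatives and their gains do not add.

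1. **Ordinary Hochberg (gamma = 1) at 0.02**, keeping the 0.03/0.05 rule. If its dependence condition is a worry, use Holm: smaller p at 0.01, then larger p at 0.02. Holm's P(both) is at most 1.0 point below ordinary Hochberg. Unlike ordinary Hochberg, it does not reject everything the current rule does: with both p-values between 0.010 and 0.011, the current rule rejects both and Holm neither.
2. **Keep gamma = 0.1 and test the clinical endpoint at 0.039** after exactly one win. The key secondary endpoint then inherits 0.039. This puts no more weight on the dependence condition than the current plan does.

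If Section 11.2.4 already contains a single-win rule, bring the synopsis into line with it. Bring the mention of key secondary endpoints in Section 8.4.3 into line with the synopsis as well.

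The cost is a sentence or two in the protocol and in the SAP amendment already planned before unblinding. No subjects are added. Because it changes primary-endpoint thresholds, the protocol change is not merely administrative and needs the regulatory and ethics approvals in Section 12.1.2. It should be made before any unblinded histology result is seen.

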# 2 LIST OF ABBREVIATIONS AND DEFINITIONS OF TERMS

Abbreviation	Term
ADA	American diabetes association
AE	Adverse events
ALT	alanine aminotransferase (SGPT)
AST	aspartate aminotransferase (SGOT)
ATP	Adenosine triphosphate
AUC	area under the <plasma> drug concentration by time curve</plasma>
4110	area under the <plasma> drug concentration by time curve for 1 dosing</plasma>
AUC 0-t	interval of a multiple-dose regimen
BMI	body mass index
BUN	blood urea nitrogen
CDMS	clinical data management system
CFR	Code of Federal Regulations
CGR	Country geographic region
CIOMS	Council for International Organizations of Medical Sciences
C max	maximum observed plasma drug concentration
CPK	creatine phosphokinase
CRF	case report form (refers to any media used to collect study data [i.e.,
Citi	paper or electronic])
CRO	contract research organization
CS	Compound Symmetry
CSC	Clinical Supply Chain
CSH	Heterogenous Compound Symmetry
CTFG	Clinical Trial Facilitation Group
DILI	Drug-induced liver injury
DMC	Data Monitoring Committee
ECG	electrocardiography, electrocardiogram
EMA	European Medicines Agency
EoS	End-of-Study
ESD	Early Study Discontinuation
ET	Early termination
ETD	Early Treatment Discontinuation
EU	European Union
FABAC	Fatty acid-bile acid conjugates
FAS	full Analysis Set
FCS	Fully Conditional Specification
FDA	US Food and Drug Administration
FMD	Flow mediated dilation
GCP	Good Clinical Practice
GDPR	General Data Protection Regulation
GGT	gamma-glutamyl transpeptidase

CONFIDENTIAL 37 of 127

# ARMOR Study

**PBPK** 

Abbreviation	Term
GI	gastrointestinal
GMP	Good manufacturing practice
H&E	Hematoxylin & Eosin
HCC	hepatocellular carcinoma
HCG	human chorionic gonadotropin
HDL	High density lipoprotein
HDPE	high density polyethylene
HIV	human immunodeficiency virus
HSC	Hepatic stellate cells
IB	Investigator's Brochure
IBD	Inflammatory bowel disease
ICF	Informed consent form
ICH	International Conference on Harmonization
IEC	Independent Ethics Committee
IMP	investigational medical product
INR	International Normalized Ratio
IRB	Institutional Review Board
ITT	intent-to-treat
LDH	lactate dehydrogenase
LSM	liver stiffness measurement
MACE	Major adverse cardiovascular events
MAD	Multiple ascending dose
MAR	Missing at random
max	maximum
MDRD	Modification of Diet in Renal Disease
MedDRA	Medical Dictionary for Regulatory Activities
MELD	Model of end-stage liver disease
MetS	Metabolic syndrome
MI	Multiple Imputations
ML	Maximum-Likelihood
MRS	Magnetic resonance spectroscopy
NAFLD	Nonalcoholic fatty liver disease
NAS	NAFLD activity score
NASH	Nonalcoholic steatohepatitis
NDA	New drug application
NITs	Non-Invasive Tests
NOAEL	No observed adverse effect level
NSAID	Non-steroidal anti-inflammatory drugs
OPTN	Organ Procurement and Transplantation Network
OTC	over-the-counter
PBC	Primary biliary cholangitis

CONFIDENTIAL 38 of 127

Physiologically based pharmacokinetic

#### **ARMOR Study**

Abbreviation	Term
PCS	Potential Clinical S

Significance

PGx pharmacogenetic(s) ы Principal Investigator PΚ pharmacokinetics

PNPLA3 Patatin-like phospholipase domain-containing protein 3

PP Per-protocol

PSC Primary sclerosing cholangitis

PT Preferred Term quality assurance QΑ QC quality control RBC red blood cell

REML Restricted Maximum-Likelihood

RTSM Randomization & Trial Supply Management

Serious adverse effects SAE SAP Statistical Analysis Plan

SCD1 Stearoyl Coenzyme A Desaturase 1

SD standard deviation

source document verification SDV

SE standard error SOC system organ class

SOP standard operating procedure SPC **Summary of Product Characteristics** 

SUSAR suspected unexpected serious adverse reaction

T2DM Type-2 diabetes mellitus

TEAE Treatment Emergent Adverse Events

time to maximum observed drug concentration tmax

TSH thyroid stimulating hormone ULN upper limit of the normal range US(A) United States (of America) UTI Urinary tract infection

WBC white blood cell

WHO World Health Organization

WHO Drug World Health Organization (WHO) drug dictionary

#### 3 INTRODUCTION

#### 3.1 Background Information

# 3.1.1 Nonalcoholic Fatty Liver Disease (NAFLD) and Nonalcoholic Steatohepatitis (NASH)

Nonalcoholic steatohepatitis (NASH) is the progressive form of nonalcoholic fatty liver disease (NAFLD), a broad term that encompasses the spectrum of fatty liver diseases ranging from simple steatosis to steatohepatitis, fibrosis and cirrhosis in individuals without significant alcohol consumption or secondary causes of steatosis. NASH is a histological definition, requiring the presence of  $\geq 5\%$  hepatic steatosis with inflammation and hepatocyte injury (ballooning) with or without fibrosis.

NAFLD is the most prevalent form of chronic liver disease in the world, paralleling the epidemic of obesity and obesity-related complications such as type 2 diabetes mellitus and metabolic syndrome. A recent meta-analysis estimated that approximately 25% of the world's population has NAFLD with a projected increase of 30% between 2016 and 2030^3. The prevalence of NASH is challenging to assess because of the biopsy-based definition. Based on the prevalence of NASH among NAFLD patients who had liver biopsies, the prevalence of NASH in the general population is estimated at 1.5% -6.45%, with a projected increase in prevalence of 15%-56% between 2016 and 2030^3. Features of metabolic syndrome are not only highly prevalent in patients with NAFLD, but also increase the risk of developing NAFLD. Patients with type 2 diabetes have a high prevalence of NAFLD, NASH and advanced stages of fibrosis.

The natural history of NAFLD is associated with liver histology at the time of presentation. Patients with simple steatosis are likely to have a benign course, while about 30-50% of patients with NASH develop progressive fibrosis, increasing their risk for cirrhosis and its complications. Both disease activity (quantified by NAFLD activity score (NAS)) and fibrosis stage affect the risk for progression to cirrhosis. Fibrosis is staged from 0-4 in relation to the extent of the scarring as follows: Stage 1, zone 3 perisinusoidal fibrosis; Stage 2, as above with portal fibrosis; Stage 3, as above with bridging fibrosis; and Stage 4, cirrhosis (NASH/CRN Brunt/Kleiner scale). The NASH CRN fibrosis staging system has been validated with respect to the intraobserver and interobserver concordance and sensitivity to change. The progression from NASH without fibrosis through various stages of fibrosis is not linear; however, NASH with fibrosis stages 2 and 3 has a significantly higher risk of progression to cirrhosis within a 10-year time frame and an increased mortality risk compared to lower stages (0-1) of disease. In fact, the presence of significant fibrosis is the best predictor of liver-related and all-cause mortality in NASH.

NASH is recognized as a major cause of chronic liver disease leading to cirrhosis, liver transplantation and hepatocellular carcinoma (HCC): NASH is the second leading etiology of cirrhosis among adults awaiting liver transplantation in the United States, while NAFLD is the third most common cause of HCC in the United States. Liver-related mortality is increased 10-fold in NASH patients compared with the general population. Additionally, NASH patients have an increased rate of cardiovascular events and neoplasia and are at a higher risk for

cardiovascular-related mortality. With the increasing prevalence of metabolic syndrome and subsequently, NAFLD, NASH, cirrhosis and complications, substantial clinical and economic burdens are inevitable.

There are currently no approved medications for NASH and management focuses on lifestyle modifications including diet and exercise. A 2018 guidance from the American Association for the Study of Liver Diseases aims for a reduction in body weight of 3%-5% to achieve improvement in steatosis and 7%-10% to improve the majority of histopathological features of NASH, including fibrosis. The guidance also recognizes the use of a number of medications available for other uses and treatment modalities such as Vitamin E, Pioglitazone and bariatric surgery for the improvement of liver disease in patients with biopsy-proven NASH and fibrosis.

#### 3.2 Aramchol

Aramchol is a novel synthetic small molecule, a conjugate of two components; cholic acid (bile acid) and arachidic acid (saturated fatty acid), linked by a stable amide group. Aramchol is the first in a new pharmacological class of fatty acid-bile acid conjugates (FABACs).

Aramchol affects Stearoyl Coenzyme A Desaturase 1 (SCD1), a key liver enzyme involved in regulating lipid metabolism. In animal models of NASH, it has been demonstrated that Aramchol down-regulates steatosis, ballooning, inflammation and fibrosis. The effect of Aramchol on fibrosis is indirect via reduction of steatosis and ballooning, and direct via reduction of collagen production from human hepatic stellate cells (HSCs).

Phase 1 studies showed a less than dose-proportional increase in the mean Aramchol exposure (1.6-fold between 200mg and 400mg and a 1.2-fold between 400mg and 600mg multiple doses), and a 2.6-fold exposure after a high-fat high-calorie meal as compared to a fast state. Dividing Aramchol to two 300mg doses Q12h resulted in an average increase of approximately 50% in the 24-hour plasma concentrations relative to the levels found with a single daily dose of 600mg Q24h.

In the Phase 2a study, a statistically-significant reduction in liver fat compared to placebo was seen after 3 months of treatment. All AEs in the treated arms were mild or moderate and none were serious. None of the patients withdrew as a result of AEs.

In the Phase 2b ARREST study, 247 subjects with biopsy-proven NASH who were overweight or obese and had prediabetes or type 2 diabetes mellitus were randomized (2:2:1) to receive once daily Aramchol 400mg (n=101), Aramchol 600mg (n=98) or placebo (n=48). Baseline histology of enrolled patients demonstrated a population with advanced disease, with 60% having stage 2 and 3 fibrosis and 70% having NAS ≥5. Subjects underwent both MRS and a biopsy at Baseline and at Week 52 (termination), which were centrally-read by an assessor blinded to treatment allocation.

Almost 90% of subjects in the active-treatment arms completed 65 weeks (52 weeks of treatment and 13 weeks of follow-up) in the study. The incidence of early termination (ET) due to AEs was very low and similar across study arms.

Results showed a statistically-significant reduction in liver fat with Aramchol 400mg (p=0.0450) but not with 600mg (p=0.0655) compared to the placebo arm, despite similarity in the magnitude of treatment effect in the 400mg and 600mg arms. A post-hoc analysis showed statistically-significant  $\geq$ 5% absolute reduction in liver fat in 47% of patients treated with Aramchol 600mg vs. 24% with placebo (p<0.028) and 37% with 400mg, suggesting a dose-response pattern.

Biopsy results, key for further assessment in a NASH pivotal study, showed that significantly more patients treated with Aramchol 600mg vs. placebo achieved NASH resolution without worsening of fibrosis (16.7% vs. 5.0%; p=0.0514); and that a larger proportion of patients showed at least a one point improvement in fibrosis stage without worsening of NASH in Aramchol 600mg vs. placebo (29.5% vs. 17.5%; p=0.2110). Only 1 patient (1.3%) progressed to cirrhosis in the Aramchol 600mg arm whereas 6 (7.5%) and 3 (7.5%) patients reached this endpoint in the 400mg and placebo arms, respectively.

Both doses significantly reduced alanine aminotransferase (ALT) (p<0.001), aspartate aminotransferase (AST) (p=0.002) and HbA1c (p<0.007) vs. placebo in a dose-dependent manner.

Aramchol continued to show a favorable safety and tolerability profile. No death was reported in the study. SAEs were reported in approximately 10% of subjects. Each SAE was reported for a single subject, SAEs were typical for the patient population and no clustering of event types was noted in the active-treatment arms. Most AEs in the study were mild and recovered.

For a detailed description of the clinical and non-clinical development program of Aramchol refer to the current IB.

